## 7.2 Medical History

Medical history data will be coded using the Medical Dictionary for Regulatory Activities (MedDRA). The actual version of the MedDRA coding dictionary will be noted in the statistical tables and clinical study report. The number and percentage of subjects in each medical history category (by MedDRA system organ class and preferred term) will be summarized overall and by treatment group. The system organ class (SOC) will be presented in alphabetical order, and the preferred terms will be presented in alphabetical order within each SOC. Subjects reporting more than one condition/diagnosis will be counted only once in each row (SOC or preferred term).

Subjects with cardiovascular history and CV risk factors will also be summarized.

### **7.3 Prior and Concomitant Medications**

Prior and concomitant medications will be summarized by generic name. A prior medication is defined as any medication taken prior to the date of the first dose of study drug. A concomitant medication is defined as any medication that started prior to the date of the first dose of study drug and continued to be taken after the first dose of study drug or any medication that started on or after the date of the first dose of study drug, but not after the date of the last dose of study drug. The number and percentage of subjects taking medications will be summarized by generic drug name based on the World Health Organization (WHO) Drug Dictionary for both prior and concomitant medications.

## **8.0 Efficacy Analyses**

### **8.1 General Considerations**

All efficacy analyses will be conducted in the ITT Population.

The primary analysis will be performed after all ongoing subjects have completed Week 16 and the database has been locked. The Week 16 evaluation will be the only and final analysis for the primary endpoint of EASI 75 and key secondary endpoints of vIGA-AD response and worst pruritus NRS 4 point reduction.

#### **Analysis of Categorical Variables**

Categorical variables will be summarized by frequencies and percentage by each treatment group. Pairwise comparison of each risankizumab group versus placebo group will be performed using Cochran-Mantel-Haenszel (CMH) test, stratified by vIGA-AD categories (moderate [vIGA-AD 3] vs. severe [vIGA-AD 4]). Point estimates and 95% CIs for the difference in proportions between each risankizumab group and placebo will be provided. Construction of CIs for the common risk difference will be based on the Mantel-Haenszel estimate adjusting for the stratification factor.

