### AD Disease Activity

- ✔ 6. Diagnosis of AD with onset of symptoms at least 2 years prior to Baseline and subject meets Hanifin and Rajka criteria.
- ✔ 7. Inadequate response to treatment with topical corticosteroids (TCS) and/or topical calcineurin inhibitors (TCI), or subject for whom topical treatments are otherwise medically inadvisable (e.g., because of side effects or safety risks). Subjects are potentially eligible after appropriate washout (10 days prior to Baseline visit).
- ✔ 8. Moderate to severe AD, defined by EASI  $\geq$  16, BSA  $\geq$  10%, and a vIGA-AD score  $\geq$  3 at the Baseline Visit.
- ✔ 9. Twice-daily use of an additive-free, bland emollient for at least 7 days prior to Baseline and throughout duration of the study is required.
- ✔ 10. Baseline weekly average of daily worst pruritus NRS  $\geq$  4. (Note: The baseline weekly average of daily worst pruritus NRS will be calculated from the 7 consecutive days immediately preceding the Baseline Visit. A minimum of 4 daily scores out of the 7 days is needed.)

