### 7.3 Statistical Analyses for Efficacy

---

Pairwise comparison of the primary endpoint and the key secondary endpoints will be conducted between each risankizumab group (risankizumab 150 mg and 300 mg, respectively) versus the placebo group using the Cochran-Mantel-Haenszel (CMH) test, stratified by baseline disease severity (moderate [vIGA-AD 3] versus severe [vIGA-AD 4]). For the analysis of the primary endpoint and key secondary endpoints, non-responder imputation (NRI) with multiple imputation (MI) to handle missing data due to COVID-19 (NRI-C) will be used as the primary approach. The non-responder imputation with no special data handling for missing data due to COVID-19 (NRI-NC) approach, observed cases (OC) approach, and MI may be conducted as appropriate sensitivity analyses to handle missing values.

Efficacy data for subjects who switch to rescue medications will be imputed from the point of rescue using an NRI approach for the primary endpoint and key secondary endpoints.

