### Worst Pruritus Numerical Rating Scale

The Worst Pruritus NRS (Appendix C) is an assessment tool used by subjects to report the intensity of pruritus during a 24-hour recall period. Subjects are asked to rate their pruritus at its worst during the past 24 hours on a scale of 0 to 10, with 0 being no itch and 10 being the worst imaginable itch.

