### **Analysis of Continuous Variables**

The model based mean and standard error will be provided for continuous variables. The Baseline and visit means will also be presented for each treatment group among subjects who have both Baseline and at least one post Baseline visit values. Treatment groups will be compared using MMRM model as described in Section 8.2 with treatment, vIGA-AD categories and the corresponding baseline value in the model. Point estimates and 95% CIs of mean change from baseline within treatment groups, and between each risankizumab treatment group and placebo will be provided.

Unless otherwise specified, any subject who is randomized based on a wrong stratum will be analyzed according to the actual stratum the subject belongs to.

"Baseline" refers to the last non-missing observation before the first administration of study drug or randomization if no study drug is given.

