### **8.2 Handling of Missing Data**

Missing data will be imputed using the following methods for the efficacy analyses:

- **Non-Responder Imputation** incorporating Multiple Imputation (MI) to handle missing data due to CCOVID-19 (NRI-C): the NRI-C analysis will categorize any subject who does not have evaluation during a pre-specified visit window (either due to missing assessment or due to early withdrawal from the study) as a non-responder for that visit. The exceptions are: 1) when the subject is a responder both before and after a specific visit window, in which case the subject will be categorized as a responder for the visit. (Only observations within the same analysis period will be used.) 2) missing data due to COVID-19 infection or logistical restriction will be handled by Multiple Imputation. In addition, all assessments after the start of rescue medications or prohibited medications will not be included in the analyses; as a result, subjects will be counted as non-responders thereafter and will not be imputed by MI. The NRI-C will be the primary approach in the analyses of categorical variables in Period A.

- A sensitivity analysis for categorical endpoints will use NRI with No special data handling for missing due to COVID-19 (NRI-NC). NRI-NC will be performed in the same way as NRI-C without the exception #2 above. That is, missing due to COVID-19 infection or logistical restriction will also be counted as non-responders. Subjects whose change/percent change from Baseline cannot be calculated because of a missing Baseline will be considered as a non-responder at all post-baseline visits in both NRI-C and NRI-NC approaches.
- Mixed-Effect Model Repeat Measurement (MMRM): The repeated measures analysis will be conducted using the mixed-effect model including observed measurements at all visits. The mixed-effect model includes the categorical fixed effects of treatment, visit and treatment-by-visit interaction, main stratification factors at randomization (vIGA-AD categories [moderate vs severe]), and the continuous fixed covariates of baseline measurement. An unstructured variance covariance matrix will be used. Parameter estimation is based on the assumption of data being missing at random and using the method of restrictive maximum likelihood (REML). The fixed effects will be used to report visit means at corresponding visits. MMRM will be the primary approach in the analysis of continuous variables in Period A.

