**Table 1. List of Primary and Key Secondary Endpoints**

Abbreviation	Endpoint
V1	Proportion of subjects achieving EASI 75 from Baseline at Week 16.
V2	Proportion of subjects achieving vIGA-AD of 0 or 1 with a reduction from Baseline of $\geq 2$ points at Week 16.
V3	Proportion of subjects achieving an improvement (reduction) of $\geq 4$ points in worst pruritus NRS from Baseline to Week 16.

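### The V3 itch-response test leaves out baseline NRS; adjusting for it could add roughly 2 to 3 points of power if response rises with baseline, and costs almost nothing if it does not

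*SAP*

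**What the plan says.** SAP 8.1 (Analysis of Categorical Variables) compares each dose with placebo by a "Cochran-Mantel-Haenszel (CMH) test, stratified by vIGA-AD categories (moderate [vIGA-AD 3] vs. severe [vIGA-AD 4" and takes the risk difference from the Mantel-Haenszel estimate over the same strata. Protocol 7.3 names the same test for the primary and key secondary endpoints, "stratified by baseline disease severity (moderate [vIGA-AD 3] versus severe [vIGA-AD 4".

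V3 (SAP 12.0, Table 1) is an improvement of 4 or more "points in worst pruritus NRS from Baseline to Week 16". Subjects rate itch "on a scale of 0 to 10, with 0 being no itch and 10 being the worst imaginable itch" (Operations Manual 3.4). Protocol 5.1, criterion 10, requires a "Baseline weekly average of daily worst pruritus NRS" of at least 4, so the value exists for every eligible subject.

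For continuous efficacy variables the SAP does adjust. Groups are compared "with treatment, vIGA-AD categories and the corresponding baseline value in the model" (SAP 8.1), the mixed model contains "the continuous fixed covariates of baseline measurement" (SAP 8.2), and "MMRM will be the primary approach in the analysis of continuous variables in Period A".

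Baseline NRS reaches V3 only through imputation. In the multiple-imputation sensitivity analysis (SAP 8.2) the baseline value is in the imputation model, but the completed datasets are again tested by CMH on vIGA-AD. SAP 8.4.3 plans no supportive secondary analyses.

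**The concern.** V3 is an absolute threshold on a bounded scale. A subject who enters at 4 must reach 0, while one who enters at 9 must reach 5. Baseline NRS is therefore a natural candidate predictor of V3 response. The one stratification factor in the test is a poor stand-in for it: vIGA-AD grades visible skin signs, and its notes tell the assessor to disregard excoriations (Operations Manual, Appendix N).

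V3 is under family-wise error control and last in the sequence. It is compared against 31 placebo subjects, and no V3 power is stated. If baseline NRS predicts response, leaving it out gives up some precision that could be had from data already collected.

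**Working it through.** **Inputs.** From the documents: 62, 62 and 31 subjects and two-sided 0.025 per dose (SAP 2.4 and 12.0), the 0 to 10 scale, and the entry threshold of 4. The documents give no baseline NRS distribution, V3 response rates or V3 power, and the transfer weights in SAP Figure 2 are not visible. I therefore assume alpha 0.025 for V3. The powers below are for the V3 test alone, not the chance that the sequence reaches it.

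**Step 1: the plan's own figure (EASI 75).** With 15% against 51%, the pooled rate is (31 × 0.15 + 62 × 0.51)/93 = 0.39.
- Null standard error: √[0.39 × 0.61 × (1/31 + 1/62)] = 0.1073.
- Alternative standard error: √[0.15 × 0.85/31 + 0.51 × 0.49/62] = 0.0902.
- Power: Φ[(0.36 − 2.241 × 0.1073)/0.0902] = Φ(1.32) = 90.7%.

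This reproduces the stated figure, which this point does not affect.

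**Step 2: the fall required.** The share of baseline that must be lost is 4/B: 4/4 = 100%, 4/6 = 67%, 4/9 = 44%, 4/10 = 40%.

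**Step 3: power if the fall is proportional to baseline.** All response inputs are assumptions. Baseline NRS is normal, truncated to 4–10. The proportional fall is normal, limited to −50% to 95%, with a lower mean on placebo. The vIGA-AD stratum has a latent correlation of 0.3 with NRS, and 10% of subjects are set to non-response. There were 5,000 trials per row.

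| Baseline mean, SD | SD of fall | Rates, active vs placebo | Correlation of response with baseline | CMH on vIGA-AD (planned) | CMH, plus NRS median split | Logistic score, vIGA-AD | Logistic score, vIGA-AD + NRS |
|---|---|---|---|---|---|---|---|
| 7, 2 | 0.35 | 41.2% vs 14.1% | 0.24 | 68.4% | 69.5% | 69.5% | 72.2% |
| 7.5, 1.5 | 0.25 | 40.0% vs 15.4% | 0.25 | 58.4% | 59.6% | 59.8% | 63.3% |
| 7, 2 | 0.25 | 35.5% vs 13.0% | 0.30 | 52.6% | 55.2% | 53.9% | 59.4% |
| 6, 2 | 0.25 | 34.2% vs 11.3% | 0.33 | 56.7% | 59.9% | 58.1% | 64.4% |
| 7, 2 | 0.20 | 37.2% vs 14.7% | 0.36 | 50.5% | 54.9% | 51.6% | 60.2% |

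The last two columns separate the covariate from the change of test. Adding NRS gains 2.7, 3.5, 5.5, 6.3 and 8.6 points, rising with the correlation. Changing from CMH to logistic on vIGA-AD alone gains 1.1 to 1.4 points.

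Other assumed proportional-fall models, with the same group sizes and alpha, gave smaller gains. CMH, logistic on vIGA-AD, and logistic plus NRS had 51.5/52.9/54.7% and 48.7/49.8/51.9%, so NRS adds 1.8 and 2.1 points. A further set gave 2.3 to 2.8 points from NRS and 0.7 to 1.4 from the change of test.

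**Step 4: power if the absolute fall is unrelated to baseline.** The same three tests gave 76.7/77.4/77.6%, so NRS adds 0.2 points. Finer CMH strata lose power here. In three runs (6,000 trials each) the planned CMH had 72.0%, 71.1% and 71.5%. A median split on NRS gave 71.3%, 69.4% and 70.2%, and three NRS bands gave 69.4%, 68.7% and 69.0%.

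**Step 5: size under the null (nominal 2.5%).** In three runs of 6,000 trials, the planned CMH gave 2.1%, 1.9% and 2.3%, and logistic with NRS gave 2.4%, 2.4% and 2.8%. The Monte Carlo standard error is √(0.025 × 0.975/6000) = 0.2 points. The planned test is valid and slightly conservative, which fits the roughly 1 point gained by changing the test alone.

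**The case against.** The strongest reply is that nothing is broken. The CMH test is valid, is named in the protocol and treats V1, V2 and V3 alike. A baseline-adjusted itch comparison already exists: change in worst pruritus NRS at Week 16 is a secondary endpoint analysed by the mixed model, though outside the multiplicity procedure. The dependence of response on baseline NRS is assumed. An adjusted test also needs a pooling rule for the COVID-19 imputations. All of this stands, and it limits the point to an inexpensive improvement.

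A reader might infer more than the documents support:

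- **That the entry threshold itself costs power.** It does not. With a baseline of at least 4, the floor never blocks a 4-point fall. Power is lost only if response probability changes with baseline NRS.
- **That the SAP adjusts every continuous analysis for baseline.** Only the Period A efficacy model does. Period B uses observed-case summaries (SAP 8.2), and no baseline covariate is stated for laboratory or vital-sign changes (SAP 9.3 and 9.4).
- **That the multiple-imputation analysis is a precedent for an adjusted test.** Baseline enters its imputation model only.
- **That chance imbalance in baseline NRS threatens the estimate.** With an SD of 1.5, one standard error of imbalance is 1.5 × √(1/31 + 1/62) = 0.33 NRS points. An imbalance of about 0.3 moves the difference by 1 to 2 points under the assumed models. The standard error of that difference is about 9 points at 15% vs 45%: √(0.15 × 0.85/31 + 0.45 × 0.55/62) = 0.090. The confidence interval already covers such variation.

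**Conclusion.** The point holds as a minor matter of efficiency, with no bias and no type I error problem. If V3 response rises with baseline NRS, adjusting for it adds roughly 2 to 3 points of power, and up to about 9 at the strongest dependence simulated (correlation 0.36). About 1 point more comes only from leaving CMH for a logistic score test and should not be credited to the covariate. If response does not depend on baseline, the covariate changes power by a few tenths of a point at most.

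These sizes rest on assumed NRS distributions, response models and an alpha of 0.025, and cannot be derived from the documents. The simulations used a score test with non-responder imputation and did not simulate multiple imputation.

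**What to change.** Before the blind is broken for the Week 16 analysis, add to SAP 8.4.1 an analysis of V3 by logistic regression on treatment, vIGA-AD stratum and continuous baseline worst pruritus NRS. Report a standardised risk difference, with its estimate and standard error pooled across the NRI-C imputations by Rubin's rules. Use the continuous covariate, not extra CMH strata: with 31 placebo subjects, finer strata gain less and can lose power.

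There are two ways to place it:

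- **As the V3 test**, only if protocol 7.3 is aligned, with the vIGA-AD-stratified CMH kept as a sensitivity analysis.
- **As a named supportive analysis**, if the protocol is left as it is. SAP 8.4.3 should then list it.

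State also which baseline V3 uses. SAP 8.1 defines Baseline as the last non-missing observation before dosing, while criterion 10 uses a 7-day average. The covariate should be the same value that defines response, and a single daily score below 4 would make response impossible.

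The cost is SAP wording and modest programming, with no new data. The downside is that V3 then has a different analysis from V1 and V2, and the protocol wording must be aligned if the adjusted analysis becomes the V3 test.

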### **Analysis of Continuous Variables**

The model based mean and standard error will be provided for continuous variables. The Baseline and visit means will also be presented for each treatment group among subjects who have both Baseline and at least one post Baseline visit values. Treatment groups will be compared using MMRM model as described in Section 8.2 with treatment, vIGA-AD categories and the corresponding baseline value in the model. Point estimates and 95% CIs of mean change from baseline within treatment groups, and between each risankizumab treatment group and placebo will be provided.

Unless otherwise specified, any subject who is randomized based on a wrong stratum will be analyzed according to the actual stratum the subject belongs to.

"Baseline" refers to the last non-missing observation before the first administration of study drug or randomization if no study drug is given.

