### 3.12 Clinical Laboratory Tests

A certified laboratory will be utilized to process and provide results for the clinical laboratory tests. Laboratory reference ranges will be obtained prior to the initiation of the study. The baseline laboratory test results for clinical assessment for a particular test will be defined as the last measurement prior to the initial dose of study drug.

Instructions regarding the collection, processing, and shipping of these samples will be provided by the central laboratory.

If a laboratory test value is outside the reference range and the investigator considers the laboratory result to be clinically significant, the investigator will:

- repeat the test to verify the out-of-range value;
- follow the out-of-range value to a satisfactory clinical resolution; or
- discontinue the subject from the study or require the subject to receive treatment; in this case, the laboratory result will be recorded as an adverse event.

Clinical Laboratory Tests		
HEMATOLOGY	CLINICAL CHEMISTRY	URINALYSIS
Hematocrit Hemoglobin Red Blood Cell (RBC) count/ Erythrocytes Mean Corpuscular Volume (MCV) White Blood Cell (WBC) count/ Leukocytes Platelet count/Thrombocytes Diff. Automatic (absolute count): Neutrophils Eosinophils Basophils Monocytes Lymphocytes Manual Differential (ONLY IF Automated Differential is abnormal): Neutrophils, bands (Stabs) Neutrophils, polymorphonuclear Eosinophils Basophils Monocytes Lymphocytes	Electrolytes Calcium Sodium Potassium Chloride Bicarbonate Substrates Glucose Blood urea nitrogen (BUN) Creatinine Estimated glomerular filtration rate (eGFR) Bilirubin Total Bilirubin Direct (if total is elevated) Bilirubin Indirect (if total is elevated) Albumin High-sensitivity C-Reactive Protein (hsCRP) Cholesterol, total a LDL Cholesterol a HDL Cholesterol a Triglycerides a FSH b	Dipstick Urinalysis Urine Nitrite Urine Protein Urine Glucose Urine Ketone Urobilinogen Urine Bilirubin Urine RBC/Erythrocytes Urine WBC/Leukocytes Urine pH Urine creatinine Urine Sediment (microscopic examination, only if urine analysis abnormal) Urine Sediment Bacteria Urine Cast in Sediment Urine Squamous Epithelial Cells Urine Sediment Crystals, Unspecified Urine Sediment RBC/Erythrocytes Urine Sediment WBC/Leukocytes Urine Urine Albumin-to-Creatinine Ratio (UACR)

Clinical Laboratory Tests		

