### 6.4 Selection and Timing of Dose for Each Subject

---

During Period A, study site staff will administer study drug (risankizumab 150 mg, risankizumab 300 mg, or matching placebo) subcutaneously at the Baseline (Study Day 0) and Week 4 visits.

During Period B, study site staff will administer either risankizumab 150 mg or risankizumab 300 mg at the Week 16, Week 28, and Week 40 visits.

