### **2.2 Study Design Overview**

This is a Phase 2, global, randomized, double-blind, placebo-controlled multicenter study that will evaluate the efficacy and safety of two dose levels, 150 mg and 300 mg respectively, of risankizumab in adult ( $\geq 18$  years of age) and adolescent (12 - 17 years of age) subjects with a confirmed diagnosis of moderate to severe AD and onset of symptoms at least 2 years prior to the Baseline Visit.

This study is comprised of an approximately 35-day screening period, a 16-week Double Blind (DB) Treatment Period A, a 36-week DB Treatment Period B, and a 20-week (140 days) Follow-up Visit.

[figure not shown]
- Period A (Baseline/Week 0 – Week 16) is a 16-week double-blind, placebo-controlled treatment period. Subjects who meet the study's eligibility criteria (Protocol Section 5.1) will be randomized at the Baseline visit to receive risankizumab 150 mg, risankizumab 300 mg or matching placebo. Study drug administration for Period A will occur at Weeks 0 and 4. The last visit in Period A is planned at Week 16 when all scheduled efficacy and safety assessments will be performed.
- In Period B (Week 16 – Week 52), subjects receiving placebo in Period A will be re-randomized at Week 16 to receive risankizumab 150 mg or risankizumab 300 mg through Week 52. Subjects originally randomized to risankizumab 150 mg or 300 mg in Period A will stay on their previously assigned treatment through Week 52. Study drug administration for Period B will occur at Weeks 16, 28 and 40.
- A follow-up telephone call visit will occur 140 days after the last dose of study drug to determine the status of any ongoing AEs/SAEs or the occurrence of any new AEs/SAEs and use of any concomitant medications.

During Period B, subjects with < EASI 50 response as compared to Baseline at the most recent prior and current scheduled visits will be allowed to use approved concomitant rescue treatment as early as at Week 24 and at any visit thereafter. Rescue treatment is limited to up to twice-daily application of topical corticosteroids.

The primary analysis will be conducted after all ongoing subjects have completed Week 16. The Week 16 evaluation is the final analysis for the primary endpoint of EASI 75 and key secondary endpoints of vIGA-AD response and worst pruritus NRS 4 point reduction. The study sites and subjects will remain blinded to treatment assignments for the duration of the study.

The schematic of the study is shown in [Figure 1](#).

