### 2.3 Treatment Assignment and Blinding

Each subject will be assigned a unique identification number by the IRT at the screening visit. Subjects who rescreen will use the same unique identification number from the initial screening visit. In addition, the IRT will assign a unique randomization number that will encode each subject's treatment group assignment according to the randomization schedule generated by the statistics department at AbbVie.

At the Baseline visit, subjects meeting eligibility criteria will be randomized in a 2:2:1 ratio to risankizumab 150 mg, risankizumab 300 mg, or matching placebo.

Randomization at Baseline will be stratified by baseline disease severity (moderate [vIGA-AD 3] vs. severe [vIGA-AD 4]) and geographic region (Japan vs. Rest of the World [RoW]).

At the Week 16 visit, subjects receiving placebo in Period A will be re-randomized in a 1:1 Ratio to receive either risankizumab 150 mg or risankizumab 300 mg through Week 52. Subjects originally randomized to risankizumab 150 mg or 300 mg in Period A will stay on their previously assigned treatment through Week 52. There is no stratification at the re-randomization at Week 16.

To maintain the blind, all risankizumab and placebo kits provided for the study will be identical in appearance. AbbVie personnel will remain blinded until the primary analysis at Week 16 is available. The study sites and subjects will remain blinded to treatment assignments for the entire duration of the study.

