## 4.0 Analysis Populations

The following population sets will be used for the analyses.

The intent-to-treat (ITT) population, which includes all randomized subjects, will be used for all efficacy analyses. Subjects will be included in the analysis according to the treatment groups that they are randomized to. Subjects who are randomized to placebo in Treatment Period A and do not continue into Treatment Period B will be excluded from the analysis in Treatment Period B.

The following populations will be used for safety analyses:

- The safety population in Period A is defined as all subjects who are randomized at Baseline and received at least one dose of study drug in Treatment Period A. Subjects are assigned to a treatment group based on the treatment actually received.
- The safety population in Period B is defined as all subjects who received at least one dose of study drug in Treatment Period B. Subjects are assigned to a treatment group based on the treatment actually received.
- An All Risankizumab Treated Population (ALL\_RZB) will consist of all subjects who received at least one dose of risankizumab in the study. This population will be used to provide a comprehensive summary of safety.

For the safety populations, subjects are assigned to a treatment group based on the "as treated" treatment group, regardless of the treatment randomized. The "as treated" is determined by the first dose subject will receive for Period A, and is determined by the first dose subject will receive for Period B.

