### **TEAEs for All RZB:**

TEAEs are defined as any event with an onset or worsening date on or after the first dose of risankizumab and no more than 140 days after the last dose of risankizumab in the study.

Events where the onset date is the same as the study drug start date are assumed to be treatment-emergent. All treatment-emergent AEs will be summarized overall, as well as by primary MedDRA SOC and Preferred Term. The SOCs will be presented in alphabetical order, and the PTs will be presented in alphabetical order within each SOC.

The number and percentage of subjects experiencing treatment-emergent AEs will be summarized.

Pre-treatment AEs will be summarized separately.

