**Table C-1. Criteria for Potentially Clinically Significant Hematology Values**

Hematology Variables	Units	Definition of Potentially Clinically Significant CTCAE (Version 4) Grade 3 or Greater
		Very Low
Hemoglobin	g/dL	< 8.0
Platelets count	10  /L	< 50.0
WBC count	10  /L	< 2.0
Neutrophils	10  /L	< 1.0
Lymphocytes	10  /L	< 0.5

Note: A post-baseline value must be more extreme than the baseline value to be considered a potentially clinically significant finding.

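### For placebo switchers, laboratory and vital-sign changes in the All-Risankizumab summaries are measured from Week 0 and so include their 16 weeks on placebo

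*SAP*

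**What the plan says.** **Baseline.** The SAP defines Baseline once, in Section 8.1 under the analysis of continuous variables: it "refers to the last non-missing observation before the first administration of study drug or randomization if no study drug is given". SAP 9.3 is consistent with this, because its rule for leaving SAE-related laboratory values out of Baseline is tied to the first dose of study drug. Operations Manual 3.12 also describes the baseline laboratory result as "defined as the last measurement prior to the initial dose of study drug", although that sentence is written for clinical assessment. Operations Manual 6.4 lists matching placebo among the study drugs.

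**Who is in the pooled population.** ALL_RZB "will consist of all subjects who received at least one dose of risankizumab in the study" (SAP 4.0). Period A "is a 16-week double-blind, placebo-controlled treatment period" (SAP 2.2), and at Week 16 "subjects receiving placebo in Period A will be re-randomized in a 1:1 Ratio to receive either risankizumab 150 mg or risankizumab 300 mg" (SAP 2.3). Placebo subjects who go on to be dosed are therefore in ALL_RZB.

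**What is summarised there.** SAP 9.1 counts laboratory and vital-sign data among the safety analyses, sends safety data to the Section 4.0 populations, and names ALL_RZB for the Week 16 analysis. SAP 9.3 and 9.4 then ask for change from baseline, laboratory shift tables and potentially clinically significant (PCS) findings. Neither section gives a baseline or a start of observation specific to ALL_RZB.

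**What starts at risankizumab.** ALL_RZB treatment-emergent events are those with onset or worsening "on or after the first dose of risankizumab and no more than 140 days after the last dose of risankizumab" (SAP 9.2.1). ALL_RZB duration of treatment in SAP 6.0 runs from the first risankizumab injection.

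**The concern.** The pooled risankizumab population is meant to describe safety on risankizumab. For switchers, the laboratory and vital-sign clock starts 16 weeks before their first risankizumab dose, so drift that arose on placebo is reported within a risankizumab summary. In the same population and the same subject, an adverse event during those weeks is left out. The laboratory and adverse-event tables for ALL_RZB then describe different intervals, and nothing in the plan tells the reader so. The same baseline carries into Period B safety summaries, where switchers sit in the dose group they were re-randomised to, beside subjects who have had risankizumab since Week 0.

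**Working it through.** **1. Group sizes.** The plan randomises 155 subjects 2:2:1. 155 × 2/5 = 62 per risankizumab group and 155 × 1/5 = 31 on placebo, as SAP 2.4 states. (The power statement there also reproduces: 0.907 for 51% against 15%, 62 against 31, two-sided 0.025, uncorrected two-proportion formula. Nothing below depends on it.)

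**2. What the change contains.** Let Y0 be a switcher's Week 0 value, Y16 the value before the first risankizumab dose, and Yt a later value. Under the stated Baseline the reported change is

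Yt − Y0 = (Yt − Y16) + (Y16 − Y0).

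The second term arose wholly on placebo. It stays in the result whether or not the on-placebo values themselves are tabulated.

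**3. Share of the pooled population.** Let c be the fraction of the 31 placebo subjects who receive risankizumab at Week 16, and let all 124 subjects randomised to risankizumab be dosed. The switcher share is 31c / (124 + 31c). The documents give no dropout rate, so c is an assumption:

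- c = 1: 31/155 = 20.0%
- c = 0.9: 27.9/151.9 = 18.4%
- c = 0.8: 24.8/148.8 = 16.7%
- c = 0.7: 21.7/145.7 = 14.9%

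**4. Effect on a pooled mean change.** This equals the share times the switchers' mean placebo-period change d. At c = 1, assumed values of d of 0.1, 0.25 and 0.5 SD give 0.02, 0.05 and 0.10 SD. With a baseline taken just before the first risankizumab dose, the contribution is 0.

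**5. Vital-sign PCS.** SAP Table C-3 requires a change from Baseline as well as a limit. High systolic pressure needs at least 160 mmHg and a rise of at least 20. Take a switcher at 140 at Week 0 and at 160 both before the Week 16 dose and later. From Week 0 the change is 160 − 140 = 20 and the later value is flagged; from Week 16 it is 0 and it is not. Reverse the placebo drift (160 at Week 0, 140 at Week 16, 160 later): the change is 0 from Week 0, not flagged, and 20 from Week 16, flagged. The error can go either way.

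**6. Laboratory PCS.** Tables C-1 and C-2 use absolute limits or multiples of ULN. Baseline enters only through the note that "A post-baseline value must be more extreme than the baseline value to be considered a potentially clinically significant finding". For post-switch values, moving the baseline changes a count only if the subject was already beyond the limit at Week 0 or at Week 16.

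**7. If on-placebo values were counted as post-baseline.** One switcher with a PCS value on placebo would add 1/155 = 0.6 percentage points. If 2%, 5% or 10% of 31 switchers had one (assumed rates), the pooled percentage would rise by 0.4, 1.0 or 2.0 points. These figures apply only under that reading.

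**8. Mismatch with exposure.** On the planned schedule (last dose Day 280, switch Day 112), ALL_RZB duration is (280 − 112) + 84 = 252 days for a switcher and (280 − 0) + 84 = 364 days for a subject on risankizumab from Day 0. Both have change measured from Day 0. The placebo time inside the change interval but outside exposure is at most 31 × 112 / 365.25 = 9.5 patient-years.

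**9. Period B.** With everyone continuing, each dose group has 15.5 switchers on average among 62 + 15.5 = 77.5 subjects, again 20%.

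**The case against.** The strongest reply is that the plan is silent rather than wrong. The Baseline sentence sits in the efficacy section, and safety has its own general considerations with no baseline. The Operations Manual sentence concerns clinical assessment, not analysis. The between-group differences in SAP 9.3 and 9.4 are against placebo, which exists only in Period A, so those paragraphs may have been written for Period A. Worst-value shifts are restricted to the treatment period, and ALL_RZB treatment starts at the first risankizumab injection, which suggests that values recorded on placebo would drop out.

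Some of this stands. A reader might infer that every Week 2 to 16 value in a switcher is counted as a risankizumab finding. No sentence says so, and the wording on worst-value shifts points the other way. Against that, SAP 9.3 sets an upper time limit on laboratory data but no lower limit at first risankizumab. The question is open.

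The rest does not remove the point. The SAP has one Baseline; its own laboratory section ties Baseline to first study drug; and SAP 9.1 expressly takes safety analyses into ALL_RZB. Dropping on-placebo values would still leave Y16 − Y0 inside every later change. For vital signs the case rests on the sentence in the efficacy section alone, but no other definition is available to a programmer.

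**Conclusion.** The point holds in a limited form. As written, switchers' change from baseline, shifts and change-based vital-sign PCS findings in ALL_RZB include their placebo-period change, and ALL_RZB adverse events and exposure do not. The size is at most 20% of the pooled population, or about 0.2 times any placebo-phase mean shift. The 20% is a ceiling that assumes every placebo subject switches.

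A reader might go further and infer that a safety signal could be masked or created. The documents do not support that: they give no value for the placebo-phase shift, laboratory PCS limits depend little on baseline, and subject-level PCS listings are planned. The effect is confined to descriptive safety summaries. Randomised Period A comparisons, treatment-emergent events, exposure and efficacy are untouched. The change should still be made, because a stated rule gives a contaminated result and the correction costs almost nothing.

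**What to change.** Add to SAP 9.1:

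- For ALL_RZB laboratory and vital-sign analyses, Baseline is the last non-missing value on or before the first risankizumab dose. For switchers this is normally the Week 16 visit value.
- State a same-day timing rule. Operations Manual 2.1 schedules haematology, chemistry and vital signs at Week 16, but explicit pre-dose timing at dosing visits is given only for PK, ADA and nAb samples (3.13). The SAP must say how a Week 16 value without a recorded time is treated.
- Only values after that dose and within 140 days of the last dose are post-baseline in ALL_RZB.
- In Period B safety summaries, use the same baseline for placebo switchers, or show switchers separately.
- Keep the Week 0 baseline for Period A and for efficacy.

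The cost is a few SAP sentences and a derived baseline and post-baseline flag. No new visits, samples or data are needed.
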